We shall cross-tabulate the pre- and post-treatment spirometry measures for study condition and group. Significance for association will be obtained by repeated measures ANOVA. The false positive and false negative rates will be estimated by exact binomial confidence limits. This is a pilot study that is seeking a promising outcome as opposed to a definitive one. We shall consider the result as promising if (a) no false positives occur and (b) the false negative rate is below 50%.

Power/Sample Size: The study will have a goal to recruit 50 CF (10 inpatient and 40 outpatient) patients. Initial data analysis to be completed after the first 25 patients have completed each test condition.

Measurable outcomes and expected timeline: We expect the PIAPD is equal to standard airway clearance in CF patients. We expect PIAPD will decrease the sense of breathing effort and increase patient sense of efficacy.

Compliance/Accountability/Regulatory

Statement of Compliance

This study will be conducted in compliance with the protocol and will be generally consistent with current Good Clinical Practices (GCP), adopting the principles of the Declaration of Helsinki and all applicable regulatory requirements (ICH E6, 45CFR46, and FDA 21CFR sections 11, 50, 56, 312).

Prior to study initiation, the protocol and the informed consent documents will be reviewed and approved by UF's Institutional Review Board (IRB). Any amendments to the protocol or consent materials will be approved before they are implemented.

Adverse Event Reporting and Safety Monitoring

In the event of an adverse event the following definitions and processes will be used/followed:

Adverse Event Definitions

In this clinical research study, an adverse event (AE) is any occurrence or worsening of an undesirable or unintended sign, symptom or disease that is associated with study procedures. As an observational study, AEs occurring between study visits will not be reported unless deemed associated with study procedures. Throughout the study, the investigator must record AEs related to study procedures on source documents regardless of severity.

Unexpected Adverse Event

An AE is considered unexpected when the nature (specificity) or severity of the event is not consistent with the risks described in the protocol or informed consent document for specific protocol-required interventions.

Grading Adverse Event Severity

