This study will utilize the National Cancer Institute (NCI) Common Toxicity Criteria for Adverse Events (CTCAE Version 3.0) to classify AE severity.

All AEs Grade 2 or greater pertaining to study procedures will be recorded on the UF IRB adverse event log, which will be reviewed by the IRB annually at continuing review. The investigator will make a determination as to the relation to participation in the study. Events will be assessed and reported in accordance with the ICH Guidelines for Good Clinical Practice and per the guidance of the DHHS Office for Human Research Protections (OHRP). Should there be an adverse event or unanticipated problem that is both serious and unexpected it will be evaluated by the PI and reported to the IRB as appropriate per current regulatory guidelines.

Informed Consent

Participants will sign their own informed consent form (or in the case of parents, they will consent for their child). This study will require written assent from minors. This study does not allow for use of legally authorized representatives or LARs. Each participant will receive a signed copy of their informed consent for their records. Participants will have the opportunity to ask questions before they sign the consent form and when a study coordinator calls them to confirm their information.

Risks and Benefits

Aside from the normal shortness of breath, which is expected as part of doing standard of care airway clearance and pulmonary function testing, there are no discomforts or risks associated with study that we know of. This research study may also include risks that are unknown at this time. If the portable airway device works as well as the standard airway clearance device, it will potentially provide a less expensive, portable alternative for patients with CF that they can use in their homes without coming to clinic and during telemedicine visits with their physician.

It is also possible, that patients may not see an improvement and may even see a worsening of their airway clearance as measured by FEV-1 while using the experimental device.

Confidentiality

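### The adverse event section calls a randomised device trial observational and filters routine event recording by relatedness, so events judged unrelated may leave no record on either device

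*Combined protocol and SAP*

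**What the plan says.** The Adverse Event Definitions section sets three rules in sequence. The definition reads "an adverse event (AE) is any occurrence or worsening of an undesirable or unintended sign, symptom or disease that is associated with study procedures". The next sentence is "As an observational study, AEs occurring between study visits will not be reported unless deemed associated with study procedures". The third says that "the investigator must record AEs related to study procedures on source documents regardless of severity".

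Grading Adverse Event Severity adds a log that the IRB sees once a year: "All AEs Grade 2 or greater pertaining to study procedures will be recorded on the UF IRB adverse event log". It then gives three provisions whose own wording contains no relatedness condition:

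- On attribution, it says: "The investigator will make a determination as to the relation to participation in the study".
- On general standards, it refers to GCP and to OHRP guidance: "Events will be assessed and reported in accordance with the ICH Guidelines for Good Clinical Practice".
- For the most important events, it sets a route to the IRB, to be used as appropriate: "Should there be an adverse event or unanticipated problem that is both serious and unexpected it will be evaluated by the PI".

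The Statement of Compliance also commits the study to ICH E6, 45CFR46 and parts of FDA 21CFR.

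Safety Endpoints lists reasons for ceasing use of the experimental device. It does not say how such a stop is recorded.

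**The concern.** A study that assigns an investigational device is interventional. The between-visit sentence gives the opposite description as its reason for a narrower reporting duty, so the stated reason fails for this design.

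The wider problem is the order of the steps. If relatedness decides whether an event enters the record at all, nobody can revisit that judgement later. The judgement belongs to the investigator, and no blinding is described. The plan also leaves open whether daily clearance with the patient's usual device, which it describes as standard care, counts as a study procedure. The filter could therefore act differently on the two devices.

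The participants are aged 6-21 with CF, whereas the earlier testing described in the Background was in healthy volunteers. Risks and Benefits accepts that some risks may be unknown. In that setting there is little basis for ruling out relatedness before an event is written down.

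**Working it through.** The plan states no figure to reproduce here, so the main check sets its sections side by side.

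**1. The label against the design.** The text before the Outpatient arm randomises participants to standard care or the experimental group. The Outpatient arm crosses them over after two weeks. The Inpatient arm randomises on Day 4 and uses the other device for the first session on Day 5. Conflicts of Interest calls the device investigational. Study Design describes a fixed order (standard device first, then the study device), but that is still an assigned intervention. No section describes an observational study.

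**2. Where relatedness is a condition.**

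| Provision | Relatedness condition in the sentence? |
|---|---|
| AE definition | Yes |
| Between-visit sentence | Yes |
| Source-document rule, any severity | Yes |
| Grade 2+ log rule | Yes |
| Investigator's determination | It is the determination itself |
| ICH GCP/OHRP sentence | No |
| Serious-and-unexpected sentence | No |

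The definition already requires association with study procedures, so the later determination is circular. It also uses another test: relation to participation in the study rather than to study procedures. The any-severity source rule and the Grade 2+ log concern different records and do not conflict with each other.

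**3. What happens to an event judged unrelated.**

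- Between visits, not both serious and unexpected: no stated recording or reporting route beyond the general commitments.
- At a visit, not both serious and unexpected: the wording allows two readings. If the definition governs, which the source-document rule supports, the result is the same. If events are recorded first and attributed afterwards, the event is captured.
- Serious and unexpected, at any time: evaluated by the PI and reported to the IRB as appropriate.

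**4. Time between outpatient contacts.** Inputs from the Outpatient arm: daily use, two weeks per device, testing twice weekly, and a Day 1 session. Assumption: a visit is a day with a study contact. Share = (days − contact days) / days. Participant-days = 40 outpatients × 2 periods × days.

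- 14 days, 4 contacts: 10/14 = 71%; 800 of 1,120 participant-days.
- 14 days, 5 contacts: 9/14 = 64%; 720 of 1,120.
- 15 days, 5 contacts: 10/15 = 67%; 800 of 1,200.

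This is the exposure window of the between-visit sentence. It is not a count of missed events.

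**5. Size of the fix.** One question about events at each existing contact, at the full planned sample of 40 outpatients and 10 inpatients:

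- Outpatients: 2 per week × 2 weeks = 4 contacts per period, or 5 if Day 1 is separate. Two periods give 8 to 10. 40 × 8 = 320; 40 × 10 = 400.
- Inpatients: one daily assessment for 9 days (leaving after Day 9) to 14 days. 10 × 9 = 90; 10 × 14 = 140.
- Total: 320 + 90 = 410, up to 400 + 140 = 540. Only the upper figure assumes that every inpatient completes 14 days. Other dropout would lower both.

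**The case against.** The strongest reply is that this is related-only AE collection in a 50-patient pilot with no AE aim and no AE analysis, and that other provisions catch what matters. Much of that stands:

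- FEV1, oximetry and Borg ratings are taken with no attribution test. Outpatients have them twice weekly on both devices, with an investigator present by telemedicine. Inpatients have them on both devices over Days 4-5. Respiratory worsening at those times would be seen.
- Safety Endpoints stops the experimental device for session symptoms and for an FEV1 fall above 10%. For inpatients it adds secondary infection and a physician's or PI's safety concern. None of these needs a formal causality test, although the discomfort trigger calls for a judgement about what is expected of such therapy.
- The general commitments to GCP, OHRP and regulatory requirements may oblige wider recording. Their content cannot be checked from the documents.

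These limit the harm but do not close the gap. Scheduled measurements and device stops are not an AE record, and nothing states that every event is recorded on both devices.

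It is also fair to say that the label does little work alone, because the definition in the preceding sentence already filters. A reader might infer that deleting the label cures the problem. It would change no recording duty. Finally, correcting the wording is a smaller step than soliciting all events, and the added grading and attribution work cannot be costed from the documents.

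**Conclusion.** The concern holds as a defect in the safety record. The label contradicts the design, and relatedness is required at entry in the definition, the between-visit sentence, the source-document rule and the Grade 2+ log. Unrelated between-visit events that are not both serious and unexpected have no specific route into the record. On the reading that the definition favours, neither do such events at visits. The plan should be changed.

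Three stronger readings are not supported:

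- A reader might infer that no event judged unrelated is ever reported. The serious-and-unexpected sentence has no relatedness condition and also covers unanticipated problems.
- A reader might infer that every reporting sentence is filtered. The GCP/OHRP sentence refers to events without qualification.
- A reader might take 64-71% as the share of events lost. Related events on those days remain reportable, and the documents give no AE rates, so the number affected cannot be computed.

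No planned analysis is affected: Statistical Analysis names spirometry only ("We shall cross-tabulate the pre- and post-treatment spirometry measures for study condition and group"). An all-cause list could give context to the tolerability ratings in Specific Aims, but that is only a possible use.

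**What to change.** In Adverse Event Definitions, delete the clause calling the study observational and the between-visit exclusion. Remove relatedness as an entry condition from the AE definition, the source-document rule and the Grade 2+ log rule.

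Ask about events since the last contact at the existing telemedicine contacts in both outpatient periods and at the existing daily inpatient assessments. Record each AE with onset date, grade and device or devices in use. Keep relatedness as a separate field, completed afterwards, with one term used throughout. Record each stop under Safety Endpoints as data, leaving the criteria as they are.

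Report descriptively. For outpatients, tabulate by device period, noting that no washout is described, so events early in the second period may carry over. For inpatients, list by hospital day and device without comparing devices: Days 1-3 are standard care only, Days 4-5 assign only the first session, Days 6-9 use the study device after stabilisation, and Days 10-14 are patient choice.

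The cost is the 410 to 540 brief questions worked out above, a longer log, and grading and attribution of all events. No new visits are needed.
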